The proposed direct comparison of tango to treadmill training is critical as it will put these two emerging forms of therapy head-to-head in order to determine their differential effects on actual locomotor performance (Aim 1), on brain activity during imagined walking (Aim 2), and on resting state functional connectivity of the locomotor control network (Aim 3) in people with PD. The combination of neuroimaging with exercise interventions is novel and will fill important gaps in our knowledge regarding basic locomotor control in PD and the mechanisms by which different exercises might convey benefit with respect to locomotor function. Previous neuroimaging work in different populations, as well as prior work in PD examining the effects of either tango or treadmill training on locomotion, sets the stage for this exciting work. Our use of different interventions along with two different neuroimaging techniques makes for a powerful and multi-faceted approach that will yield an extremely rich data set capable of addressing multiple gaps in our current knowledge.

B2 Rationale for this Study

Effective treatment of locomotor dysfunction in PD is essential, as gait difficulty is an early and major contributor to disability. The proposed study will provide important insights into the effects of different modes of exercise on locomotor function in PD, filling current knowledge gaps and guiding future design and delivery of optimal exercise interventions. This work is innovative because it: 1) uses a community-based exercise approach, 2) examines dance as a novel form of exercise and directly compares it to traditional treadmill training and *stretching*, 3) tests participants OFF medication to allow more accurate assessment of disease severity, and 4) utilizes two distinct neuroimaging approaches, in conjunction with interventions, to explore potential mechanisms of the effects of exercise on both brain function and brain connectivity.

C Study Objectives

C1 Primary Aim

SPECIFIC AIM 1: To determine the effects of tango, treadmill training, and stretching (control) exercise on locomotor function and other aspects of PD. The primary variable for this aim is gait velocity. Additional gait variables of interest are stride

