Based upon our previous intervention studies, we anticipate an attrition rate of approximately 15-20% due to dropouts or failure to complete the required minimum of 85% of classes.

2.f When and How to Withdraw Subjects

Individuals may withdraw at any time during the duration of the study

2.g Data Collection and Follow-up for Withdrawn Subjects

No follow-up will be completed for withdrawn subjects

E3 Study Drug

None

F Study Procedures

F1 Screening for Eligibility

Possible participants will be screened via a phone interview. The screening process will identify if the individual meets the inclusion criteria stated above and does not meet any of the exclusion criteria.

F2 Schedule of Measurements

Time requirements:

Screening phone call - 15-20 minutes - on medication

Pre-Intervention Evaluation - 4.5 hours - off medication

3 exercise sessions per week for 12 weeks - 1 hour each - on medication

Post Intervention Evaluation Visit - 4 hours - off medication

Follow-Up Evaluation - 12 weeks after conclusion of exercise class - 2 hours (no fMRI) - off medication

Screening phone call

Following the consent process we will complete an MRI screening form. If the individual is not excluded from completing an MRI scanning session we will continue with the screening process.

In addition, all eligible participants must be able to perform the imagined gait tasks in the MRI at or above a previously determined threshold. All participants will complete the Kinesthetic and Visual Imagery Questionnaire (KVIQ-20) (Malouin, et al, 2007) with an additional four question “imagined” gait task assessment (Pickett, Peterson & [name], 2012). The KVIQ-20 is used to assess vividness of mental imagery during motor tasks and has been previously used with PD patients (Heremans, et al, 2011). Participants with a mean KVIQ-20 + gait subsection score more than one standard deviation below the mean of an age matched healthy cohort (data recently collected in [name] lab) will be excluded from the study.

Any individual who is accepted for the study based on the above will be given a packet of questionnaires to complete at home and continue on following the procedure below. This portion will be completed with a researcher who is blinded to the individual’s group assignment. The specific questionnaires that will be included in the packet are as follows:

Epworth Sleepiness Scale

Non-Motor Symptom Questionnaire

Stages of Readiness to Exercise Questionnaire

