Wechsler Test of Adult Reading (WTAR)
Spatial Delayed Response Task (SDR)
Nback Working Memory Test (Nback)
Trail Making Test
Stroop Test
Go-No-Go (GNG)
Verbal Fluency
RMswitch task
Frontal Systems Behavior Scale (FrSBe)

All individuals will complete the clinical assessments listed below as well as gait and balance testing consisting of the following (approximately 1 hour):

RMswitch task
Go-No-Go (GNG)
Spatial Delayed Response Task (SDR)
Nback Working Memory Test (Nback)
Mini Mental Status Exam (MMSE)
The New Freezing of Gait Questionnaire (nFOG_Q)
Mini BESTest
The Smell Threshold Kit
Movement Disorder Society Unified Parkinson Disease Rating Scale (MDS-UPDRS)
Five times sit to stand (5xSTS) - 6 minute walk (6MWT) - 9 Hole Peg Test (9HPT)
PDQ-39
Forward preferred speed, forward fast, backward, tandem and dual task walking on a GAITRite computerized walkway system.
Spatiotemporal gait assessment will be completed simultaneously with the GaitRITE assessment.

F7 Visit 3 – Follow-up

A follow-up visit will be scheduled for 12 weeks after the final exercise class has been completed.

All individuals will complete the following battery of questionnaires and assessments (approximately 90 minutes):

Montreal Cognitive Assessment
Wechsler Test of Adult Reading (WTAR)
Spatial Delayed Response Task (SDR)
Nback Working Memory Test (Nback)
Trail Making Test
Stroop Test
Go-No-Go (GNG)
Verbal Fluency
RMswitch task
Frontal Systems Behavior Scale (FrSBe)

All individuals will complete the clinical assessments listed below as well as gait and balance testing consisting of the following (approximately 1 hour):

RMswitch task
Go-No-Go (GNG)
Spatial Delayed Response Task (SDR)
Nback Working Memory Test (Nback)
Mini Mental Status Exam (MMSE)
The New Freezing of Gait Questionnaire (nFOG_Q)
Mini BESTest
The Smell Threshold Kit
Movement Disorder Society Unified Parkinson Disease Rating Scale (MDS-UPDRS)
Five times sit to stand (5xSTS) - 6 minute walk (6MWT) - 9 Hole Peg Test (9HPT)
PDQ-39
Forward preferred speed, forward fast, backward, tandem and dual task walking on a GAITRite computerized walkway system.
Spatiotemporal gait assessment will be completed simultaneously with the GaitRITE assessment.

F8 Safety and Adverse Events

8.a Safety and Compliance Monitoring

8.b Medical Monitoring

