Effects of medication withdrawal will be monitored via patient report and if the effects are too severe, participation in the study will be terminated prior to the second day of "off medication" testing.

8.c Definitions of Adverse Events

An adverse event is any patient reported

8.d Classification of Events

We do not anticipate any adverse events; however, the following procedures will be followed to minimize the risk.

- a) Temporary Worsening of Parkinson's symptoms. A temporary worsening of Parkinson's disease symptoms may result from not taking anti-Parkinson's medication for study evaluations. Once the individual resumes taking their medication, symptoms should return to their typical levels. Effects of medication withdrawal will be monitored and if the effects are too severe, participation in the study will be terminated prior to the second day of "off medication" testing .
- b) Loss of confidentiality. Loss of confidentiality is highly unlikely. To safeguard against this, we will comply with all HIPAA regulations. Data will not be identified by subject name. All data will be coded, and code sheets will be stored in locked files.
- c) Stumbling during locomotion. Subjects will be closely attended by a physical therapist during walking. Walking will be performed in a large, open space and the therapist will be prepared to assist subjects who may stumble. It is therefore unlikely that subjects will experience falls during testing or will be injured as the result of a fall.
- d) Falling into safety harness. During testing on the treadmill, subjects will wear a modified parachute harness connected to an overhead beam that is rated to support heavy loads. A subject who falls will be supported fully by the harness and is therefore unlikely to be injured. Subjects will also be able to hold the support guides which will help them to stabilize balance during treadmill testing. In addition, the treadmill will be equipped with redundant safety features to prevent subject injury and allow immediate cessation of treadmill movement at the touch of a button.

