For **Aim 1**, we will employ a repeated measures ANOVA with group (tango, treadmill, and *stretching*) and time (pre-intervention, post-intervention, and *follow-up*) as factors to determine whether and how these interventions impact gait velocity, our primary variable for Aim 1. Similar analyses will also be performed for secondary variables of interest, including the MDS-UPDRS-III, mini-BESTest, and PDQ-39. *As a secondary analysis for gait velocity, MDS-UPDRS-III, and mini-BESTest, we will determine percent difference between OFF and ON medication values at pre-intervention and post-intervention time points and compare these difference values using RM ANOVAs with group and time as factors. (If prescribed medications change over the course of the study then levodopa equivalent daily dose will be included as a covariate in these analyses.) This will allow us to determine if response to medications was different before vs. after intervention and whether this effect differed between groups.* Analyses will be conducted using NCSS software (NCSS, LLC, Kaysville, UT). All imaging analyses will be conducted using Brain Voyager (Brain Innovation, Maastricht, The Netherlands) and custom written Matlab (MathWorks, Natick, MA) software. For **Aim 2**, we will apply random effects general linear model analysis using forward and backward imagined tasks as individual contrasts. A false discovery rate (FDR) correction will be used to compensate for multiple comparisons. BOLD signal changes within the previously specified regions of interest will be compared for pre- and post-intervention conditions. Additionally, the three groups will be compared to each other in the post-intervention condition using RFX ANCOVA. For **Aim 3**, we will use an independent component analysis (ICA) to examine the strength of the correlation coefficients for anatomical regions identified as part of the locomotor control network. The strength of these correlations before vs. after intervention will be compared via two-tailed RM ANOVAs with group and time as factors. Finally, we will correlate BOLD signal changes during the imagined walking tasks (Aim 2) and changes in connectivity (Aim 3) with changes in motor performance.

G4 Missing Outcome Data

For Aim 1 dropouts will be handled utilizing intent to treat analyses with the last observation carried forward. Dropouts will be excluded from analyses in Aims 2 and 3 as full imaging data are needed from two time points.

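### Aim 1 fills the visits of unmeasured leavers by last observation carried forward alone, with no sensitivity analysis: a minor weakness that is cheap to improve

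*Combined protocol and SAP*

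**What the plan says.** All references are to the combined protocol and SAP.

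- **Primary variable and analysis.** C1: "The primary variable for this aim is gait velocity". G3 analyses it by repeated-measures ANOVA with group (three arms) and time (pre, post, follow-up) "as factors to determine whether and how these interventions impact gait velocity, our primary variable for Aim 1". Both later visits are therefore in the primary test. F7 sets the last one: "A follow-up visit will be scheduled for 12 weeks after the final exercise class has been completed".
- **Missing data.** G4, and G1 in the same words: "For Aim 1 dropouts will be handled utilizing intent to treat analyses with the last observation carried forward". No other method, missingness assumption or sensitivity analysis appears anywhere.
- **Withdrawal.** E2 2.f: "Individuals may withdraw at any time during the duration of the study". E2 2.g: "No follow-up will be completed for withdrawn subjects".
- **Expected loss.** E2 2.e and G1: "we anticipate an attrition rate of approximately 15-20% due to dropouts or failure to complete the required minimum of 85% of classes". No split by arm or by time is given.

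**The concern.** The two rules act together: 2.g stops the measurement, and G4 then supplies a number in its place. A loss before the post visit has its baseline value copied into both later visits, so it counts as exactly zero change. A loss after the post visit has that value copied to follow-up, so it counts as full retention. Since withdrawn people are not measured again, the trial's own data cannot show whether either value is near the truth.

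At the stated attrition this could concern up to 18-24 of 120 people (0.15 to 0.20 x 120), or 6-8 per arm. The direction of error is not fixed. Early losses pull a real gain towards zero, a decline among leavers is hidden, and late losses can overstate retention. What is at stake is how far the Aim 1 estimate can be trusted, not whether the trial can detect its design difference.

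**Working it through.** **1. Inputs.** From G1: SD 0.1 m/s, design difference 0.1 m/s (effect size 0.4), 27 per group for 89% power at two-sided 0.05, 40 recruited per group, attrition 15-20%. Timing of loss, loss by arm, leavers' true change, visit correlation and return rate are not in the documents. They are assumed below.

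**2. The plan's own figure.** For a one-way ANOVA F test with 3 groups, f = 0.4 and N = 81, the noncentrality is 0.4² x 81 = 12.96 and power is 89.5%, against 89% stated. It reproduces. (Read as a standardised two-group difference, 0.4 would give only 31%, so 0.4 is Cohen's f.)

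**3. Room for attrition.** 40 x 0.80 = 32 and 40 x 0.85 = 34 remain per arm, giving about 94-95% power. Suppose instead that all loss is early and carrying forward shrinks every effect to 80-85% of its size. Then f is 0.32-0.34, and power with 40 per arm is still about 88-92%.

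**4. Test size.** Simulated group x time F test on carried-forward data: 3 x 40 people, 3 visits, SD 0.1, visit correlation 0.5-0.8, 10,000 runs per cell.
- No change in any arm, equal 15-20% loss: 4.4-5.4%.
- Common gain of 0.10 in all arms, loss of 15/17.5/20%: 5.5-5.9% if loss counts vary at random, 1.9-3.5% if they are fixed.

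A re-run of the 20% and 15/17.5/20% cells with all loss before the post visit agreed within simulation error.

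**5. Error at the post visit.** Let p be the share lost early, f the share of leavers measured, and g the leavers' true mean change. Completers gain 0.10 and control 0.
- Truth = (1-p) x 0.10 + p x g
- LOCF = (1-p) x 0.10 + p x f x g
- Mixed model = [(1-p) x 0.10 + p x f x g] / [1 - p(1-f)]

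With f = 0 the LOCF error in an arm is p x |g|. For |g| up to 0.1 this is at most 0.15 x 0.1 = 0.015 to 0.20 x 0.1 = 0.020 m/s. A contrast between arms carries the difference of the two arms' errors, which cancels if loss and leavers' change are the same in both.

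With p = 0.20 and f = 0:

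| g (m/s) | Truth | LOCF | Mixed model |
|---|---|---|---|
| 0.10 | 0.100 | 0.080 | 0.100 |
| 0.05 | 0.090 | 0.080 | 0.100 |
| 0 | 0.080 | 0.080 | 0.100 |
| -0.10 | 0.060 | 0.080 | 0.100 |

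Neither method responds to g when no leaver is measured. They bracket the truth for g between 0 and 0.10, and both overstate if leavers decline.

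**6. What measuring leavers buys.** With p = 0.20 and g = 0, LOCF and the truth are both 0.080.
- 10% return: 0.08/0.82 = 0.098, gap 0.018
- 25% return: 0.08/0.85 = 0.094, gap 0.014
- 50% return: 0.08/0.90 = 0.089, gap 0.009

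The gap with no return is 0.020.

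**7. Follow-up visit.** The LOCF error from late losses is the share lost late x the fade since the post visit. If a gain of 0.10 has gone completely and 5-10% are lost late (assumed), 0.005-0.010 m/s is reported as retained.

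**The case against.** The strongest reply is that little is shown to be wrong. Power and test size hold, and if leavers gain nothing, LOCF is exact at the post visit while the mixed model is 0.020 too high. With 40 per arm, SD 0.1 and correlation 0.5-0.8, the standard error of a two-arm change contrast is sqrt[(2/40) x 2 x 0.01 x (1 - correlation)] = 0.014-0.022 m/s. Even a 50% return narrows the gap by only 0.011, which is less than one standard error. All of this stands. It is why the point is minor and why the mixed model should not be used without the sensitivity analysis.

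The definition of withdrawn is also open. Section 2.e lists dropouts separately from people under 85% attendance, and nothing says that stopping classes means withdrawal from the study. Some of the 15-20% may be measured already, so the figures above are upper limits.

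A reader might infer that F8 8.b makes loss depend on the outcome: "Effects of medication withdrawal will be monitored via patient report and if the effects are too severe, participation in the study will be terminated". The documents do not carry that far. The rule applies before the second OFF test day, no frequency is given, and E1 has behavioural measures taken ON as well as OFF. Inviting people back would not reach these exits either; only the sensitivity range covers them. This is no comment on the 8.b rule.

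**Conclusion.** The point holds as a minor, cheap improvement. LOCF is the only Aim 1 rule, withdrawn people are not measured, and nothing tests the assumption. The error at the post visit is at most 0.015-0.020 m/s per arm, on the assumptions that all 15-20% attrition is early and unmeasured and that leavers' change lies within -0.1 to +0.1 m/s. The textual facts are certain. The size of the benefit from the fix is not, because it depends on a return rate that the documents do not give.

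Three stronger readings are not supported. The trial is not underpowered on this account. The primary test is not shown to be invalid: markedly unequal loss could inflate it, but no loss by arm is given. A mixed model is not better in every case, as the row for leavers who gain nothing shows.

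**What to change.** 1. **G1 and G4.** Analyse all observed visits in the randomised arm with a likelihood-based mixed model (group, visit, group x visit) in place of LOCF alone. Pair it with a prespecified sensitivity analysis. First use baseline carried forward for unmeasured leavers, which equals LOCF for early losses but not for late ones. Then vary their change over a range such as -0.1 to +0.1 m/s. With nobody measured, that range moves one arm's mean by 0.15 to 0.20 x 0.2 = 0.030-0.040 m/s in total.
2. **E2 2.g.** Invite people who stop classes to the scheduled post and follow-up behavioural assessments without MRI, unless they have withdrawn consent or their participation has ended under 8.b.
3. **Clarification only.** Say whether attendance under 85% (0.85 x 36 = 30.6, so fewer than 31 of 36 classes) makes someone withdrawn. Reconcile 2.g with F8 8.f, which follows patients for adverse events for 12 weeks after their final session.

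**Cost.** Items 1 and 3 are wording and analysis, and no extra participants are needed. For item 2, the 4 h post visit without the 90-minute MRI takes 2.5 h. Adding the 2 h follow-up stated in F2 gives 4.5 h each, or 81-108 h for 18-24 people. If the batteries itemised in F7 (about 90 minutes plus 1 hour) hold, it is 5 h each, or 90-120 h. These visits are already scheduled for all 120. ON testing time and staff cost cannot be derived from the documents. The $50 follow-up payment in J2 comes to $900-$1,200, already planned; J2 names no payment for a post visit without MRI.

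**Downsides.** Leavers would be asked to attend OFF-medication visits, and withholding medication overnight is a listed risk in E2 2.d. Some will decline. The main result then relies on data missing at random for those still unmeasured, and the effect estimate may be smaller.
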